11.2 Laboratory analysis

11.2.1 Molecular diagnosis

NAMRU-6 laboratory will perform real-time reverse transcriptase polymerase chain reaction (RT-PCR) assays to ascertain infection with influenza A or B viruses and identify influenza A subtype and influenza B lineage. Testing will be completed using US CDC protocol and with primers, probes, and reagents provided by US CDC. A subset of aliquots may be sent to a US CDC reference laboratory in order to confirm and further validate local RT-PCR results.

Additional testing for other respiratory pathogens (e.g. RSV, parainfluenza viruses, human metapneumovirus, adenoviruses, and coronaviruses) might also be conducted. A subset of all viruses will undergo virus isolation. Also, some viruses/specimens will have molecular characterization with genetic sequencing and other assays to detect genetic markers and antiviral resistance. Remaining aliquots of study specimens with future use authorization may be sent to a US CDC-designated facility for additional virus characterization, banking and storage for at least 3 years; no specimens will contain personal identifiers. Samples without future use authorization will be destroyed after the study is finished.

11.2.2 Serology analysis

Samples will be processed and then frozen at -20°C. Specimens will be stored at the local CDC-approved local laboratory for serologic testing and then will be shipped to the US CDC laboratory for serologic testing at the end of the study. Hemagglutination inhibition (HI) assay will be run in duplicate using a CDC-approved protocol. Standard procedures typically include preparing a turkey (for A/H1N1 and influenza Bs) or guinea pig red blood cells (RBC) (for A/H3N2) suspension and treating serum samples with receptor-destroying enzyme to remove nonspecific inhibitors. Nonspecific agglutinins are removed by serum adsorption with packed RBCs. Serum is diluted 2-fold starting from 1:10. The HI titer is the reciprocal of the serum dilution in the last well with complete hemagglutination inhibition.

The panel of influenza viruses to be included in the HI assay will be determined depending on locally circulating viruses during enrollment and historically, including viruses in circulation during the previous 2-6 years.

Samples will be also shipped to US CDC labs for additional testing with additional immunological assays for influenza and other respiratory pathogens (e.g. RSV, parainfluenza viruses, human metapneumovirus, adenoviruses, and coronaviruses) or other agents that cause respiratory diseases such as bacteria, as well as for the biorepository.

11.2.3 Optional Sub-study

As an optional sub-study, we will examine indicators of cell-mediated immune (CMI) response to influenza vaccination. This part of the study, which is optional to participants, will require collection of additional blood samples, pre-vaccination and at 7 and 28 days post-vaccination.

Participants who consent to participate in this optional part of the study, will provide an additional 20mL heparinized whole blood at enrollment before vaccination and at 7 and 28 (in a range from day 21 to day 35) days post-vaccination for extraction of peripheral blood mononuclear cells (PBMCs), which can be used for assays focused on cell-mediated immunity (CMI). Extraction of PBMCs will be performed at NAMRU6 laboratory or at the laboratory assigned by NAMRU6 and then samples will be shipped to a US. CDC approved laboratory to assess cell-mediated immunity.

The separate heparin-treated blood specimens collected for CMI response testing will be kept at room temperature in transit and delivered to the laboratory within 2-4 hours of collection if possible (though standard procedures allow for up to 12 hour delays). PBMCs will be isolated from the heparinized whole blood using standard procedures and cryopreserved in liquid nitrogen until further analysis.

12. INVESTIGATIONAL AND CONTROL PRODUCT

Investigational product:

- Generic name: FLUAD[®] QuadInfluenza Vaccine, Adjuvanted (Seqirus)
- Dosage and Administration: a single 0.5 mL for intramuscular injection
- Lot/batch/serial number: TBD
- Expiration date: TBD
- Potency: TBD
- Formulations: SH 2022 quadrivalent formulation as per World Health Organization (WHO) recommendation:
 - A/Victoria/2570/2019 (H1N1)pdm09-like virus 15micrograms HA (hemagglutinin per dose);
 - A/Darwin /9/2021 (H3N2)-like virus 15micrograms HA (hemagglutinin per dose;
 - B/Austria/1359417/2021(B/Victoria lineage)-like virus 15micrograms HA (hemagglutinin per dose);
 - B/Phuket/3073/2013 (B/Yamagata lineage)-like virus 15micrograms HA (hemagglutinin per dose).

FLUAD[®] Quad (Influenza Vaccine, Adjuvanted) is a sterile suspension for intramuscular injection, is a quadrivalent, inactivated influenza vaccine prepared from virus propagated in the allantoic cavity of embryonated hens' eggs inoculated with a specific type of influenza virus suspension. Each dose contains hemagglutinin (HA) from each of the four influenza strains recommended for the 2022 influenza season and also contains MF59C.1 adjuvant (), a squalene based oil-in-water emulsion. Each strain is harvested

and clarified separately by centrifugation and filtration prior to inactivation with formaldehyde. The inactivated virus is concentrated and purified by zonal centrifugation. The surface antigens, hemagglutinin and neuraminidase, are obtained from the influenza virus particle by further centrifugation in the presence of cetyltrimethylammonium bromide (CTAB).

- Storage conditions: 2-8 degrees Celsius
- Disposal and Accountability: The Principal Investigator or a designee is responsible for maintaining complete investigational products inventory records accounting for receipt, storage, dispensation, and final disposition using forms supplied by (or local equivalents approved by) CDC or designee (See appendix P). These records will be reviewed by CDC representatives or designee. At the conclusion of the trial, all vaccine vials of investigational products, used and unused, will be destroyed at the hospital site upon consent by CDC.

This vaccine has not been assessed and authorized for its use and commercialization in Peru by the regulatory office of the Ministry of Health (DIGEMID by its acronyms in Spanish)

Control product:

- Generic name: VaxigripTetra dose standard Quadrivalent vaccine (Sanofi Pasteur)
- Dosage and Administration: a single 0.5 mL for intramuscular injection
- Lot/batch/serial number: TBD
- Expiration date: TBD
- Potency: TBD
- Formulations: SH 2022 quadrivalent formulation as per World Health Organization (WHO) recommendation:
 - A/Victoria/2570/2019 (H1N1)pdm09-like virus 15micrograms HA (hemagglutinin per dose);
 - A/Darwin /2671/2019 (H3N2)-like virus 15micrograms HA (hemagglutinin per dose);
 - B/Austria/1359417/2021 (B/Victoria lineage)-like virus 15micrograms HA (hemagglutinin per dose);

- B/Phuket/3073/2013(B/Yamagata lineage)-like virus 15micrograms HA (hemagglutinin per dose). VaxigripTetraQuadrivalent (Influenza Vaccine) for intramuscular injection is an inactivated influenza vaccine, prepared from influenza viruses propagated in embryonated chicken eggs. The virus-containing allantoic fluid is harvested and inactivated with formaldehyde. Influenza virus is concentrated and purified in a linear sucrose density gradient solution using a continuous flow centrifuge. The virus is then chemically disrupted using a non-ionic surfactant, octylphenol ethoxylate (Triton® X-100), producing a split virus. The split virus is further purified and then suspended in sodium phosphatebuffered isotonic sodium chloride solution.

- Storage conditions: 2-8 degrees Celsius
- Disposal and Accountability: The Principal Investigator or a designee is responsible for maintaining complete investigational products inventory records accounting for receipt, storage, dispensation, and final disposition using forms supplied by (or local equivalents approved by) CDC or designee (See appendix P). These records will be reviewed by CDC representatives or designee. At the conclusion of the trial, all vaccine vials of investigational products, used and unused, will be destroyed at the hospital site upon consent by CDC.

This vaccine has been assessed and authorized for his use and commercialization in Peru by the regulatory office of the Ministry of Health (DIGEMID by its acronyms in Spanish)

13. ASSESSMENT OF SAFETY

Study staff will contact participants on day $3(\pm 2)$ and day $7(\pm 2)$ to ask about potential adverse effects or reactions participants might have developed after vaccination. This evaluation may be both face-to-face and virtual, especially considering that, due to the effects of the pandemic, face-to-face assistance could be affected. In addition, participants may report adverse events at any time to study personnel. Contact information will be provided at enrollment. Any adverse event will be investigated (Appendix O - INS Adverse Event Report Format) and participants will be referred to an independent physician for evaluation. The management and reporting of adverse events will be carried out taking into account the definitions and procedures detailed below.

13.1. Adverse events: definitions and procedures for recording, evaluating,

monitoring and reporting

13.1.1. Definition of an adverse event (AE)

An AE is any event or situation that is detrimental to the health of the research subject, to whom an investigational product is being administered, and that does not necessarily have a causal relationship with its administration. Therefore, an adverse event (AE) can be any unfavorable and unintended sign; including an abnormal laboratory finding, symptom, or disease temporarily associated with the use of an investigational product; whether or not it is related to it. All AEs fall into one of two categories: "not serious" or "serious".

- A. Some examples of an AE include the following:
 - Any abnormal results in laboratory tests (hematology, clinical chemistry, or urinalysis) or other safety evaluations (eg, ECG, X-rays, vital sign measurements), including those that are worse from baseline, deemed clinically significant by the investigator's medical and scientific judgment (i.e. not related to a known comorbid condition).
 - Exacerbation of a chronic or intermittent pre-existing condition, including an increase in the frequency or intensity of the condition.
 - New conditions detected or diagnosed after administration of study vaccine, even though they may have been present before the start of the trial.
 - Signs, symptoms or the clinical sequela of a suspected drug interaction.
 - Signs, symptoms, or clinical sequela of a suspected overdose of study vaccine or a vaccine / concomitant drug.
 - An adverse effect of the study vaccine or a vaccine / concomitant drug.
 - An accident or injury.
- B. Events that DO NOT meet the definition of AE:
 - The medical or surgical procedures or other therapeutic interventions themselves are not AE, but the condition for which the surgery / intervention is required is an AE and must be documented accordingly.
 - The planned surgical measures and the condition (s) leading to these measures are not AE if the condition (s) was known prior to the observation period (see below) and it didn't get worse during the trial.

In the latter case, the condition should be reported as a medical history.

- Situations in which there was no detrimental medical event (eg, social and / or convenience income in a hospital).
- Predicted daily fluctuations of pre-existing disease (s) or condition (s) present or detected at the start of the trial that are not worsening.

Death is not considered an AE, but a result.

13.1.2. Definition of a SAE

If an event is not an EA as defined above, then it cannot be an EAS, even if the seriousness conditions are met.

An SAE is defined as any detrimental medical event that, at any dose:

- Causes death.
- Is life threatening: The term "life threatening" in the definition of "serious" refers to an event in which a subject was at risk of dying at the time the event occurred. It does not refer to an event that hypothetically could have led to death if it had been more serious.
- Requires hospitalization or the extension of an existing hospitalization. In general, hospitalization means that the subject stayed (usually involving a stay of at least one night) in the hospital or emergency room for observation and / or for treatment that would not have been adequate in the doctor's office or in an outpatient setting. Complications that occur during hospitalization are EA. If a complication prolongs hospitalization or meets any other criteria for seriousness, it will be considered serious. If there are doubts as to whether there was a "hospitalization" or if it was necessary, the AE should be considered serious.

Hospitalization for scheduled treatment of a pre-existing condition that did not get worse from the start is not considered an AE.

• Causes a persistent disability / incapacity: The term disability means a significant impairment in a person's ability to perform normal life activities.

This definition does not seek to include experiences of relatively minor medical relevance, such as uncomplicated headache, nausea, vomiting, diarrhea, flu, and accidental trauma (for example, sprained ankle) that could hinder or prevent daily activities. , but not a significant disorder.

- It is a congenital anomaly / It is a congenital anomaly / congenital malformation in the subject's offspring.
- It is a significant medical event: Medical or scientific judgment should be used when deciding whether a SAE report is appropriate in other situations, such as major medical events that may not pose an immediate risk to life or result in death or hospitalization, but which may endanger the subject or may require medical or surgical intervention to avoid one of the other outcomes described in the definition above. In general, these events should be considered serious.

Some examples of such events include invasive cancers or malignant neoplasms, intensive treatment in an emergency room or at home for allergic bronchospasm, blood dyscrasias or seizures that do not require hospitalization, or the development of dependence or drug abuse.

13.1.3. Assessment of intensity and causality

A. Intensity evaluation:

The investigator will assess the intensity of each AE and SAE reported during the trial and assign it to one of the following categories.

- Absent (grade 0): no AE
- Mild (grade 1): an event easily tolerated by the subject, causing minimal discomfort and not interfering with daily activities.
- Severe (grade 3): an event that prevents normal daily activities. An AE that is assessed as severe should not be confused with an EAS. Severe is a category used to rate the intensity of an event; and both AE and SAE can be classified as serious.
- B. Causality Assessment

The investigator is obliged to evaluate the relationship between the study vaccine and each incidence of each AE / SAE. Causation will be determined as follows:

- **Related**: there is a reasonable causal relationship between study vaccine and AD.
- Unrelated: there is no reasonable causal relationship between study vaccine and AD.

A "reasonable possibility" of a relationship implies that there are facts, evidence, and / or arguments that suggest a causal relationship, rather than a relationship that cannot be ruled out.

The investigator will use clinical judgment to determine the relationship. Alternative causes, such as underlying disease (s), concomitant therapy or vaccine, and other risk factors, as well as the temporal relationship of the event to administration of the study vaccine, will be considered and investigated.

The investigator will also consult the Investigator's Manual in their assessment.

For each AE / SAE, the investigator **should** document in the medical record that he / she has reviewed the AE / SAE and provided an assessment of causation.

There may be situations where an EAS has occurred and the investigator has minimal information to include in the initial report for the sponsor. However, it is very important that the investigator always performs an assessment of the causality of each event prior to the initial transmission of the EAS data to the sponsor.

Investigator can change their opinion on causation based on follow-up information and submit SAE follow-up report with updated causation assessment.

Assessment of causality is one of the criteria used in determining regulatory reporting requirements.

All symptoms described by the patient at the express request of the local investigator are considered related to vaccination.

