8. JUSTIFICATION

An adjuvanted quadrivalent inactivated influenza vaccine (aQIV), FLUAD[®] Quad (Seqirus) has been licensed in 38 countries including the USA since 2015 for use in persons aged 65 years and older [1, 2].

FLUAD[®] Quad is a standard-dose influenza vaccine that contains an adjuvant named MF59. This adjuvant is naturally found in humans and enhances immune response to vaccination [1, 3].

Studies have shown a significantly improved immunogenicity and seroprotection among adults aged \geq 65 years who received an AD influenza vaccine when compared to those vaccinated with a non-adjuvanted SD [4, 5]. A randomized study by Cowling et al (2019) [4] showed that MF-59 vaccine, among other enhanced vaccines, presented significantly higher proportion of participants who achieved a 4-fold or greater rise in postvaccination titers from day 0 to Day 30, with a postvaccination titer \geq 40, a significantly higher geometric mean titer at Day 30, compared to those who received a standard dose vaccine. In addition, they observed a trend rise of vaccine-specific T-cells at 7 and 30 days postvaccination with MF59. Studies have also shown effectiveness of adjuvanted influenza vaccine against influenza-associated outcomes [6].

Studies not noted safety concerns, and while AD vaccine has been associated with increased reactogenicity compared with non-adjuvanted SD vaccine in some studies, these symptoms have generally been reported to be mild or moderate and self-limited [1, 3, 4, 7, 8].

Not all people who receive SD influenza vaccines develop a protective antibody response to influenza virus infections. Vaccinee characteristics can be associated with poor immunogenic response to influenza vaccination [9-17].

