10.13 Study outcomes

The primary outcome to be measured will be seroconversion at day 28 after vaccination. Seroconversion will be defined as having a haemagglutination inhibition (HI) geometric mean titre (GMT) of \geq 1:40 in the case the pre-vaccination HI GMT <1:10 or having a four-fold rise in titre in the case the pre-vaccination HI GMT \geq 1:10. We will also measure HI GMT at the end of season. Seroprotection will be defined as having an HI GMT \geq 1:40.

Other outcomes that will be measured include:

-reactogenicity to vaccination

-acceptability of AD influenza vaccination

-acute respiratory illness (ARI)

-ARI-associated outcomes (absenteeism, medical visits, hospitalization, other)

-laboratory-confirmed influenza and other respiratory pathogens

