Laboratory- confirmed influenza illness rates in HCP receiving AD	Clinical	Comparison of persons who did and did not become sick with influenza after receiving the AD or SD	Person became sick with influenza after receiving AD or SD vaccine Person did not become	Nasal swab specimen tests positive for influenza by PCR	Quantitative Discrete	PCR assay (laboratory)
vaccine		vaccine	sick with influenza after receiving AD or SD vaccine	Nasal swab specimen tests negative for influenza by PCR		

Secondary Objective 6: To assess the adverse events among HCP receiving SD and AD influenza vaccines

				Criterios de	Tipo de	Instrumento de
Variable	Dimensión	Indicador	Valores	medición	variable/indicador	medición
	(Dimension)	(Indicator)	(Values)	(Measurement criteria)	(Type of variable/indicator)	(Measurement instrument)
Adverse events in HCP receiving AD vs. SD vaccine	Anticipated (Clinical)	Local reactions: pain on vaccination site, swelling, lump itching, bruising	Yes	Person had a local and/or systemic reaction(s) after receiving AD or SD vaccine	Quantitative Discrete	Post-vaccination surveillance via follow-up visits and monitoring (calls, surveys)

	AND/OR Systemic reactions: fever (≥38°C), muscle ache, joint pain, headache, malaise, fatigue, weakness, sweating, shivering	No	Person did not have a local and/or systemic reaction(s) after receiving AD or SD vaccine		
	Death, life- threatening adverse event, hospitalization or prolongation of existing	Yes	Person had a serious adverse event after receiving the AD or SD vaccine		Post-vaccination surveillance via
Serious, Unanticipated (Clinical)	hospitalization, a persistent or significant incapacity affecting normal life activities, and other unanticipated event that seriously impacts the health of participants	No	Person did not have a serious adverse event after receiving the AD or SD vaccine	Quantitative Discrete	follow-up visits, monitoring (calls, surveys), and hospitalizations

Below we describe the statistical tests that we will perform to address each primary and secondary objective, highlighting which study population will be included for each analysis. All statistical tests will be performed with a significance level of 5% and a statistical power of 80%.

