5) To evaluate laboratory-confirmed influenza illness rates in the group receiving AD influenza vaccination compared to the group receiving SD influenza vaccination. Using data collected through active surveillance, we will calculate incidence densities and use descriptive statistics and Z-test to assess differences in the proportion of HCPs who had laboratory-confirmed influenza (as determined by PCR on nasal swab samples) during the period of the clinical trial among the HCP who received the influenza vaccines AD vs. SD. A Cox regression model will be used to adjust the risk of developing influenza between both groups according to demographic and occupational characteristics. Health personnel participating in the clinical trial will be included as a study population for these analyzes.

6) To assess the adverse events among HCP receiving SD and AD influenza vaccines. Using data collected through active surveillance, we will use descriptive statistics and the Z test to assess the differences in the proportions of adverse events (anticipated and serious) between the HCP who received the AD and SD

influenza vaccines. All health personnel participating in the clinical trial will be included as a study population for these analyzes.

Table 1: Summary of Analysis by Endpoints and Analysis Populations.

OBJECTIVE	VALUATION CRITERIA	STATISTICAL TEST	POPULATION OF ANALYSIS
Primary Efficacy Analysis			
To determine if the AD influenza vaccine generates superior immunogenicity than the vaccine against SD influence without adjuvant among the HCP.	Immunogenicity - superior serumconversion of AD vaccine versus SD vaccine in HCP.	Wilcoxon signed rank test.	PP population
Secondary Efficacy Analysis			
To compare the post-vaccine immune response, in approximately 28 days after vaccination and at the end of the influenza season, among the HCP with a history of influenza infection confirmed by PCR result during any of the 6 years during the previous cohort study (2016 to 2021).	Post-vaccination immune responses, approximately 28 days after vaccination and at the end of the season, among HCPs with a history of PCR-confirmed influenza infection	Wilcoxon signed rank test.	ITTm1

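### The planned safety comparison reduces all anticipated reactions to one yes/no, so it will not separate local from systemic reactions, fever from arm pain, or mild from more intense; the grading scale as supplied also lacks a grade 2

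*Combined protocol and SAP*

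**What the plan says.** **Outcome and premise.** Section 10.13 lists "reactogenicity to vaccination" and the acceptability of the adjuvanted (AD) vaccine among the other outcomes, without a definition, grade or time window. Section 8 acknowledges more reactogenicity with AD than with the standard-dose (SD) vaccine in some studies, and adds that "these symptoms have generally been reported to be mild or moderate and self-limited".

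**Endpoint.** The objective 6 table in section 11.1 has two rows.
- The anticipated row lists local reactions (such as pain and itching) and systemic reactions (such as fever of 38°C or more and headache), joined by AND/OR. The Yes value is "Person had a local and/or systemic reaction(s) after receiving AD or SD vaccine".
- The second row is labelled as serious and unanticipated. Its Yes value is any serious adverse event after vaccination.

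**Analysis.** The text for objective 6 plans descriptive statistics and a Z test for "differences in the proportions of adverse events (anticipated and serious". The summary table of analyses gives the criterion simply as the frequency of AEs, in the safety population.

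**Grading.** Section 13.1.3 states: "The investigator will assess the intensity of each AE and SAE reported during the trial and assign it to one of the following categories". The categories that follow in the supplied text are "Absent (grade 0): no AE", "Mild (grade 1): an event easily tolerated by the subject, causing minimal discomfort and not interfering with daily activities" and "Severe (grade 3): an event that prevents normal daily activities". Section 13.1.6 repeats that severity is evaluated for each AE, and AEs go on the eCRF by sign, symptom or diagnosis.

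**The concern.** The plan's own account of AD's drawback is about the kind and intensity of reactions, and section 9 expects health authorities to weigh AD against SD for health care personnel. For that they need to know which reactions are more frequent and how intense they are. A single any-reaction proportion is dominated by whichever reaction is commonest. It can leave an excess of a rarer systemic reaction unseen, or present an excess of mild arm pain as a general safety difference.

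The scale adds a second difficulty. Section 8 describes reactions as mild or moderate, yet the listed categories contain no moderate. Someone whose muscle ache slows them at work but does not stop them is neither grade 1, which must not interfere with activity, nor grade 3, which must prevent it.

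**Working it through.** The plan states no reaction rate, margin or power for safety, so there is no figure to reproduce. The check is a reading of the text plus an illustration.

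**1. What is collected against what is analysed**

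| Feature | Collected | In the objective 6 analysis |
|---|---|---|
| Intensity | Yes, each AE (13.1.3, 13.1.6) | No |
| Individual symptom | Yes, AE term on the eCRF (13.1.6); memory aid (10.6.4) | No, pooled |
| Local versus systemic | Yes, injection-site evaluation (section 3); separable by symptom | No, joined by AND/OR |
| Serious or not | Yes (13.1.6) | Yes |
| Non-serious unsolicited AE | Yes, to trial end (13.1.4, 13.1.7) | Unclear: outside the objective 6 text, possibly inside the summary table |

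**2. The scale**

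The supplied grades are 0, 1 and 3. Grade 1 requires no interference with daily activities and grade 3 requires that they be prevented. Interference short of prevention has no category, although each AE must be put in one.

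**3. Illustration of pooling**

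The arm size of 400 is from section 10.4. All rates are assumed: pain 60% in both arms, fever 1% SD and 4% AD, the two independent.

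P(any) = 1 − (1 − pain)(1 − fever)
- SD: 1 − 0.40 × 0.99 = 0.604
- AD: 1 − 0.40 × 0.96 = 0.616

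z = difference / √[p̄(1 − p̄) × 2/400], where p̄ is the mean of the two proportions.
- Any reaction: 0.012 / √(0.61 × 0.39 × 2/400) = 0.012 / 0.0345 = 0.35, p = 0.73
- Fever alone: 0.03 / √(0.025 × 0.975 × 2/400) = 0.03 / 0.0110 = 2.72, p = 0.007

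**4. The same fever rates when AD also raises pain**

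Assume pain 50% SD and 60% AD.
- Any reaction, SD: 1 − 0.50 × 0.99 = 0.505; AD: 1 − 0.40 × 0.96 = 0.616
- z = 0.111 / √(0.5605 × 0.4395 × 2/400) = 0.111 / 0.0351 = 3.16, p = 0.002
- Pain alone: z = 0.10 / √(0.55 × 0.45 × 2/400) = 0.10 / 0.0352 = 2.84, p = 0.004

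The pooled test now rejects, but pain alone would produce nearly the same result. The reader still learns nothing about fever.

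**5. What a comparison by grade could detect**

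Two-sided 5% test, 400 per arm, assumed rates:

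power = Φ{[d − 1.96 √(p̄(1 − p̄) × 2/400)] / √[(p₁(1 − p₁) + p₂(1 − p₂))/400]}, where d = |p₁ − p₂|.
- Grade 2 or higher, 20% versus 10%: 97.8%
- Grade 3, 5% versus 1%: 91.4%; 4% versus 1%: 77.7%; 3% versus 1%: 52.4%; 2% versus 1%: 21.3%

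If any-reaction rates are equal in the two arms, the pooled test rejects only at its 5% level, whatever the mix of grades. Splitting by grade therefore recovers information on moderate reactions, but small differences in grade 3 would remain uncertain.

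**The case against.** **The data exist.** A reader might infer that the trial cannot show how intense AD's reactions are. The documents do not support that. Every AE is graded and named, and there are Day 3 and Day 7 assessments, an injection-site evaluation and a daily record card. Fever could be separated from pain, and grade 1 from grade 3, after the fact. What stands is that none of this is in the planned analysis.

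**The grade 2 gap may not be real.** Numbering of 0, 1, 3 implies that a grade 2 was intended, and a line could have been lost when the PDF was read. The form contents (Appendices H, I, O and U) are not in the supplied text and may already carry a full scale. This part is therefore a check, not an established omission. It has no bearing on the endpoint.

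**Non-serious unsolicited AEs.** A reader might infer that they are analysed nowhere. The summary table's criterion, frequency of AEs, can be read to include them. What stands is that the objective 6 text is narrower than that table.

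**SAEs.** The row label suggests that only unanticipated SAEs count, but the criterion takes any SAE. The label needs correcting; there is no gap in the rule.

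**Bias.** Rounding up or down from a missing grade need not favour an arm: staff are to be blinded and allocation is 1:1 at each site. The loss is of resolution.

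**Priority.** Safety is a secondary objective of an immunogenicity trial, and the fever example rests on chosen rates with equal pain in both arms. Both are fair, and they limit the weight of the point. They do not justify collecting grades that no analysis uses when the remedy costs so little.

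**Conclusion.** The concern holds in limited form. As written, the objective 6 comparison will not distinguish local from systemic reactions, one symptom from another, or mild from more intense reactions, although the data to do so are collected. This rests on the text alone and needs no assumed rate.

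The missing grade 2 is conditional. If the source document contains it, that part falls away; if not, the scale cannot record the moderate reactions that section 8 describes.

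No size can be taken from the documents. The contrast between p = 0.73 and p = 0.007 depends on 400 per arm, equal pain rates, independence and the fever rates chosen. With pain also higher under AD the pooled test rejects, though without identifying the cause. This should be changed before analysis; it does not threaten the primary objective.

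**What to change.** 1. In the objective 6 table, replace the pooled yes/no with any local reaction, any systemic reaction and each listed reaction, each tabulated by arm and by the participant's maximum grade.
2. Reconcile the objective 6 table, the objective 6 text and the summary table so that non-serious unsolicited AEs are explicitly analysed. Relabel the SAE row so that it plainly covers all SAEs.
3. Check section 13.1.3 against the source document. If grade 2 is absent, state it with a definition covering events that interfere with daily activities without preventing them.
4. Confirm that the AE form, the Day 3 and Day 7 forms and the daily record card use the same scale.

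The cost is a line in the scale if it is missing, possibly some form options, and more rows in the safety tables. No visit or participant is added. The downside is a larger number of safety comparisons, which should be presented as descriptive, with estimates and confidence intervals.
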